10.2.7.2. Dosing During Surgery

For subjects who require emergent or elective surgery during the study period, the target FIX levels for the proposed procedure will be those deemed appropriate by the Investigator for the type of surgery to be performed. Recommendations for the appropriate dosing regimen of rFIXFc during the surgery may be discussed between the Investigator and Medical Monitor taking factors such as standard doses of FIX for the type of surgery, the clinical status of the subject, and incremental recovery data for the subject into consideration.

CONFIDENTIAL

The information contained herein may not be used, disclosed, or published without the written consent of Bioerativ
Therapeutics Inc

10.2.7.3. Rehabilitation Period

If surgery-related dosing is to be continued during postoperative rehabilitation, the dose of rFIXFc will be adjusted to achieve a trough at a sufficient level to maintain hemostasis, including during physical therapy.

Subjects will return to their pre-surgery regimen once all dosing for the postoperative period has been completed.

10.3. Treatment Precautions

Epinephrine for subcutaneous injection, antihistamine for IV injection, and any other medications and resuscitation equipment for the emergency management of anaphylactic reactions must be available in the room where the subject's first injection of rFIXFc (commercially available rFIXFc and/or study drug) is being performed. The subject's first injection of rFIXFc study drug after the confirmation of eligibility must be performed by the Investigator or by qualified medical personnel identified by the Investigator. In addition, the subjects or parents/caregivers (as appropriate) will be provided with specific instructions by the Investigator on what to do should such an event occur while at home, including how to seek emergency medical treatment.

10.4. Modification of Dose and/or Treatment Schedule

Information on modifications to the dose and treatment schedule can be found in Section [7.3.2](#).

10.5. Non-Medical Treatment With rFIXFc

During the study, subjects' parents/caregivers or subjects may attend training sessions on administration of rFIXFc. Administration of rFIXFc for training purposes will be considered nonmedical treatment. Such training is permitted and must be recorded in the EPD. However, subject/parent/caregiver administration with the first dose of rFIXFc must be performed under supervision in the clinic. Data from this time period will be excluded from the analysis of consumption.

10.6. End of Treatment

Any subject who reaches at least 50 EDs of rFIXFc, is considered to have completed treatment.

For subjects undergoing ITI with rFIXFc, the end of treatment occurs when:

1. The subject has achieved successful immune tolerance as defined in Section [10.2.6](#).

OR

2. The subject has completed 24 months on an ITI regimen without achieving successful immune tolerance.

CONFIDENTIAL

The information contained herein may not be used, disclosed, or published without the written consent of Bioverativ
Therapeutics Inc

Individual subjects may also have to end treatment because 1 of the following has occurred:

1. The subject has met criteria for early withdrawal (Section 11).
2. Study stopping rules have been met (Section 7.4).
3. EOS has been reached (Section 7.5).

Upon ending treatment for any of the reasons described above, the subject will return to the site for the ET/EOS visit.

The Final Safety Follow-up Visit (by telephone or in person) will be conducted within 14 (+7) days after the last dose of rFIXFc to assess the subject's status, collect AEs and/or SAEs, collect concomitant medications and procedures, and follow up on open AEs and SAEs (Section 4.2.2.1).

10.7. Treatment Compliance

Compliance with treatment dosing is to be monitored and recorded by site staff. The instructions provided in the DHA must be followed, as summarized in Section 10.1.1 of this protocol.

For the doses that will be administered at the study site, the study treatment will be administered under controlled conditions by the investigational staff; therefore, full compliance with study treatment is anticipated.

For between visit administration, subjects' parents or caregivers will administer (or older children will self-administer) rFIXFc and will record treatment in the EPD. The EPD will be reviewed during periodic calls to the subject's parents/caregiver and at each clinic visit.

10.8. Concomitant Therapy and Procedures

The use of concomitant therapies or procedures defined below must be recorded on the subject's eCRF according to instructions for eCRF completion. AEs related to administration of these therapies or procedures must be documented on the appropriate eCRF.

10.8.1. Concomitant Therapy

A concomitant therapy is any drug or substance administered from 30 days prior to the Screening Visit through the Final Safety Follow-up Visit/Telephone Call. For subjects who are receiving breast milk, the mother will provide consent to collect the concomitant medications that she is taking (as part of the main parental consent). The mother's concomitant medications will not be collected if the breast milk is derived from a source other than the mother, if the mother will not consent, or if the mother is no longer breastfeeding. Refusal of the mother to provide consent for collection of her concomitant medication data will not affect the eligibility of the subject to participate in the study. The list of disallowed concomitant medications below does not apply to the mother's medications.

CONFIDENTIAL

The information contained herein may not be used, disclosed, or published without the written consent of Bioerativ
Therapeutics Inc

Subjects (and their parents/caregivers) should be instructed that the subject not start taking any new medications, including nonprescription drugs and herbal preparations, unless they have received permission from the Investigator.

Allowed Concomitant Therapy

Therapy considered necessary for the subject's welfare, including routine immunizations, may be given at the discretion of the Investigator. Immunomodulatory therapies are allowed at the Investigator's discretion if administered as part of an approved ITI regimen. Bypassing agents (e.g., aPCC [FEIBA], rFVIIa [NovoSeven]) are allowed in subjects with confirmed or suspected inhibitors as outlined in Section 10.2.6.4. All such therapy must be recorded in the eCRF. The prophylactic use of bypassing agents in subjects with confirmed or suspected inhibitors must be communicated to the Sponsor Medical Monitor with documentation of rationale.

Disallowed Concomitant Therapy

No other drug under investigation may be used concomitantly with the study treatment. Subjects are not allowed to participate concurrently in another clinical study.

The following concomitant medications are not permitted during the study:

- acetylsalicylic acid
- current systemic treatment with chemotherapy and/or other immunosuppressant drugs. Use of steroids for treatment of asthma or management of acute allergic episodes or otherwise life-threatening episodes is allowed. Treatment in these circumstances should not exceed a 14-day duration.
- any other FIX product (exception allowed for 1 emergency or accidental use)

10.8.2. Concomitant Procedures

A concomitant procedure is any therapeutic intervention (e.g., surgery/biopsy, physical therapy) or diagnostic assessment (e.g., blood gas measurement, bacterial cultures) performed from 30 days prior to Screening Visit until the Final Safety Follow-up Visit/Telephone Call. The reason for all concomitant procedures performed during the study will be documented in the medical records and recorded in the eCRF.

10.9. Continuation of Treatment

No further provisions are made for access to the study treatment. If rFIXFc is proven to be beneficial, all regulatory requirements regarding poststudy access will be met.

CONFIDENTIAL

The information contained herein may not be used, disclosed, or published without the written consent of Bioverativ Therapeutics Inc

11. WITHDRAWAL OF SUBJECTS FROM THE STUDY

A subject must permanently discontinue study treatment and be withdrawn from the study if any of the following occur:

- The subject is found to have FIX activity >2% or a positive inhibitor based on central laboratory results from samples collected during the screening period
- Development of a Grade 2 or greater allergic drug reaction in association with the administration of rFIXFc, as defined below by the Recommendations for Grading of Acute and Subacute Toxic Effects on the World Health Organization (WHO) scale [[WHO Handbook 1979](#)]:
 - Grade 2: bronchospasm; no parenteral therapy needed
 - Grade 3: bronchospasm; parenteral therapy required
 - Grade 4: anaphylaxis
- Development of a positive inhibitor as defined in Section 10.2.4, either a low titer inhibitor with bleeding that is no longer reliably controlled with rFIXFc or a high titer inhibitor, and opting not to undergo or continue ITI
- Use of FIX products other than rFIXFc (exception allowed for 1 emergency or accidental use); a further exception is the use of activated prothrombin complex concentrate for subjects developing inhibitors (see Section 10.2.6.6)
- Development of any condition that precludes subjects from complying with the study procedures
- A medical emergency that necessitates discontinuation of treatment
- Judgment of the Investigator: a subject may have treatment permanently discontinued if, in the opinion of the Investigator, it is not in the subject's best interest to continue with the study treatment
- The parent/legal guardian can withdraw the subject from the study, or the subject can withdraw from the study, at will at any time
- At the discretion of the Investigator or Sponsor for noncompliance

The reason for the subject's withdrawal from the study must be recorded in the subject's eCRF.

For any subject who is not responding to treatment with rFIXFc, as determined by the Investigator, a decision will be made with the Sponsor whether to continue the subject in the study.

CONFIDENTIAL

The information contained herein may not be used, disclosed, or published without the written consent of Bioerativ
Therapeutics Inc

If the decision is made to withdraw the subject from the study, the ET/EOS Visit assessments will be performed as described in Section [4.2](#).

CONFIDENTIAL

The information contained herein may not be used, disclosed, or published without the written consent of Bioverativ
Therapeutics Inc

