- ^d Medical and surgical history includes any significant medical condition and/or any significant surgical histories, plus the following: HIV infection status (if positive, viral load, cluster of differentiation 4 [CD4] count, and platelets; based on laboratory results within the last 6 months), hepatitis B infection status, hepatitis C infection status, medication history, and any other congenital immunodeficiency. Medical history should also include any dosing with commercially available rFIXFc for bleeding episodes between 28 days prior to Screening and meeting all eligibility criteria.
- ^e After screening, physical examination should be performed at least annually; more frequent physical examinations may be performed at the Investigator's discretion, according to their standard of care.
- ^f Vital signs include blood pressure, pulse rate, respiratory rate, and temperature (°C). Postdose assessments following in-clinic injections should be taken approximately 10 minutes after the end of the rFIXFc injection.
- ^g Hematology includes white blood cell count and differential, red blood cell, hemoglobin, hematocrit, and platelet count.
- ^h Blood chemistry includes sodium, potassium, chloride, total protein, total bilirubin, gamma glutamyl transferase, aspartate aminotransferase, alanine aminotransferase, alkaline phosphatase, blood urea nitrogen, serum creatinine, and glucose.
- ⁱ Sample to be used to determine seropositivity at Screening, should subject be diagnosed with HIV, hepatitis B, or hepatitis C during the study.
- ^j Washout prior to sample collection for inhibitor and anti-rFIXFc antibody tests should be at least 72 hours (including prior to collection of the Screening sample, if there was prior dosing with FIX). Samples for anti-rFIXFc antibody testing will be collected at the same timepoint when any samples are collected for inhibitor testing, including confirmatory and unscheduled inhibitor tests. An unscheduled visit may be required to obtain samples to confirm a positive inhibitor test result.
- ^k See minimum criteria for enrollment, Section 8.3.
- ^l The predose sample collection for FIX activity, anti-rFIXFc antibody, and inhibitor testing are only required for subjects who received at least 1 dose of any product containing FIX, including commercially available rFIXFc or a blood product transfusion, prior to the dose for the baseline IR assessment.

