^q For subjects who are receiving breast milk, maternal concomitant medications will also be collected at the same time points as other concomitant therapies, unless the breast milk is derived from a source other than the mother or the mother has not consented.

Note: Additional unscheduled visits may be necessary during the study to test for inhibitors, test for recovery, repeat safety assessments, or repeat any blood sampling if required for study purposes or for local standard of care.

CONFIDENTIAL

The information contained herein may not be used, disclosed, or published without the written consent of Bioverativ
Therapeutics Inc

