7. STUDY DESIGN

7.1. Study Overview

This is an open-label, single-arm, multicenter study evaluating the safety and efficacy of rFIXFc in previously untreated subjects with severe hemophilia B when used according to local standard of care. For the purpose of this study, a PUP is defined as a subject who has not had prior exposure to FIX concentrates, except for up to 3 injections of commercially available rFIXFc between 28 days prior to the first Screening Visit and the confirmation of eligibility. Following the confirmation of eligibility, administration of commercially available rFIXFc is no longer allowed and only rFIXFc labeled for study use is to be administered (henceforth, the latter supply will be described as rFIXFc study drug, to distinguish it from commercially available rFIXFc). Subjects with a documented plasma FIX activity of $\leq 2\%$ may be enrolled on the basis of local laboratory results and may receive study drug after samples for factor IX activity level and inhibitors have been obtained for testing at the central laboratory. However, any such subject must be withdrawn if the central laboratory screening results indicate factor IX activity level $> 2\%$ or a positive inhibitor. Baseline incremental recovery (IR) assessments described in Section 4.2.1 should be performed as soon as practicable once all eligibility criteria have been met and the subject has been enrolled. The Baseline IR Visit activities may be completed on the same day as Screening, or they may be completed as a part of a separate visit or at an unscheduled visit.

Following confirmation of eligibility and enrollment, the Investigator has the option to treat a subject episodically (on-demand) prior to initiating a prophylaxis regimen. The duration of episodic treatment is at the Investigator's discretion, in accordance with local standard of care. At least 20 previously untreated subjects are planned to complete the study after reaching at least 50 EDs with rFIXFc. One ED is defined as a 24-hour period in which a subject receives 1 or more doses of rFIXFc, with the time of the first injection of rFIXFc defined as the start of the ED.

Surgery is allowed during the study. See Section 10.2.7 for further instructions.

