8. SELECTION OF SUBJECTS

8.1. Inclusion Criteria

To be eligible to participate in this study, candidates must meet the following eligibility criteria at the time of screening, or at the timepoint specified in the individual eligibility criterion listed:

1. Ability of the subject or the subject's legally authorized representative (e.g., their parent or legal guardian) to understand the purpose and risks of the study and provide signed and dated informed consent and authorization to use confidential health information, and/or to provide assent, in accordance with national and local subject privacy regulations.
2. Male, age <18 years at the time of informed consent.
3. Weight ≥ 3.5 kg.
4. Severe hemophilia B defined as ≤ 2 IU/dL ($\leq 2\%$) endogenous FIX documented with local laboratory results either in the medical record or as tested during the Screening Period. Any subject who is enrolled based on results of the local laboratory (from the medical record or at screening) must be withdrawn if the central laboratory screening results indicate a baseline FIX activity level $>2\%$ of normal.

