9.1.2. Bleeding Episodes Prior to Meeting All Eligibility Criteria

In the event that a subject sustains a bleeding episode that requires treatment prior to meeting all eligibility criteria, the subject's parent/legal guardian should contact the site immediately. Bleeding episodes that occur prior to the subject meeting all eligibility criteria may be treated with up to 3 doses of commercially available rFIXFc using Appendix A as a guideline. If the subject receives more than 3 injections of commercially available rFIXFc during the period from 28 days prior to Screening to the confirmation of eligibility, the subject will be considered a screen failure. If rFIXFc is not commercially available, the subject should be treated with another FIX concentrate and will be considered a screen failure.

Any bleeding episode that occurs after the subject has met all eligibility criteria should be treated with rFIXFc study drug.

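### The mandatory withdrawal rule for central screening FIX above 2% makes no exception for the commercial rFIXFc that the protocol allows beforehand, so residual drug can remove an eligible child

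*Protocol*

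**What the plan says.** Section 11 of the protocol lists as a ground for mandatory, permanent withdrawal: "The subject is found to have FIX activity >2% or a positive inhibitor based on central laboratory results", from samples taken during screening. The Synopsis (Study Design) and Sections 7.1, 7.3.1, 8.3 and 9.1.1 repeat the rule. All of them use measured activity, and none gives an exception.

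Inclusion criterion 4 (Section 8.1) defines severe disease by endogenous FIX of 2 IU/dL or less. Its own withdrawal sentence says a subject "must be withdrawn if the central laboratory screening results indicate a baseline FIX activity level $>2\%$ of normal". Baseline is not defined there as free of drug.

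Earlier exposure to rFIXFc is allowed. Section 7.1 defines a previously untreated patient as one with no FIX concentrate exposure "except for up to 3 injections of commercially available rFIXFc between 28 days prior to the first Screening Visit and the confirmation of eligibility". Section 9.1.2 adds: "Bleeding episodes that occur prior to the subject meeting all eligibility criteria may be treated with up to 3 doses of commercially available rFIXFc", with Appendix A as the dose guide.

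In the screening schedule (Section 4.2.1), the FIX activity sample carries only footnote k, "See minimum criteria for enrollment, Section 8.3", and Section 8.3 states no washout. Footnote j sets at least 72 hours for the inhibitor and antibody samples, "including prior to collection of the Screening sample, if there was prior dosing with FIX".

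**The concern.** The protocol foresees that a child may have had rFIXFc before the screening draw. It then reads that draw against a 2% limit meant for the child's own factor. A one-stage assay on a sample with circulating rFIXFc measures both together. Read literally, the rule removes a child with severe haemophilia B because of a treatment the protocol permitted.

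If he has already had study drug, he stays in the primary inhibitor denominator (SAP 9.4.3.2) with follow-up cut short. He also no longer counts towards the target of 20 subjects with 50 exposure days, from about 30 enrolled. The screening FIX category in SAP 6.2.2.1 (below 1%, 1% or above) can be distorted in the same way, but that row is descriptive only.

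**Working it through.** The documents give no time above 2 IU/dL, so there is no stated figure to reproduce. The time can be derived from protocol Table 1.

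**Inputs, age under 6 years (geometric means):** incremental recovery (IR) 0.590 IU/dL per IU/kg; dose-normalised AUC 22.71; MRT 83.65 h; terminal half-life 66.49 h. The table is internally consistent: CL × MRT = 4.365 × 83.65 = 365.1 mL/kg, which equals the stated Vss.

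**Doses.** Dose = target peak / IR. The Appendix A targets give 25/0.590 = 42.4, 50/0.590 = 84.7 and 100/0.590 = 169.5 IU/kg. A dose of 50 IU/kg peaks at 29.5 IU/dL and 100 IU/kg at 59 IU/dL.

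**Model.** Level per IU/kg = A·exp(−a·t) + B·exp(−b·t), with b = ln 2/66.49 = 0.01042/h, solved from
- A + B = 0.590
- A/a + B/b = 22.71
- A/a² + B/b² = 22.71 × 83.65

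This gives A = 0.3864, a = 0.1216/h, B = 0.2036.

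Simple decay from the peak is not usable. It implies an AUC of 0.590 × 66.49/ln 2 = 56.6, which is 2.49 times the stated 22.71, and it would overstate the time (10.8 days after 50 IU/kg).

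**Time to 2 IU/dL.** The first term is negligible by then, so t = ln(dose × 0.2036/2)/0.01042. For 50 IU/kg: ln(10.18/2)/0.01042 = 156 h = 6.5 days.

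| Single dose (IU/kg) | Level at 72 h (IU/dL) | Days above 2 IU/dL, zero endogenous FIX |
|---|---|---|
| 42.4 (25% peak) | 4.1 | 5.8 |
| 50 | 4.8 | 6.5 |
| 84.7 (50% peak) | 8.2 | 8.6 |
| 100 | 9.6 | 9.3 |
| 169.5 (100% peak) | 16.3 | 11.4 |

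**Sensitivity.**
- With an assumed 1.0 IU/dL endogenous FIX, the drug must fall to 1.0 IU/dL: 8.6 days (42.4 IU/kg) and 9.3 days (50 IU/kg). For 100 IU/kg, ln(20.36/1)/0.01042 = 289 h = 12.0 days.
- Three 100%-peak doses at an assumed 48 h spacing, zero endogenous FIX: 14.1 days after the last dose.
- Half-life of 60, 72 or 79.14 h with the other inputs held: 6.7, 6.3 and 5.9 days after 50 IU/kg. At the lower confidence limit of 55.86 h the model has no solution.
- Ages 6 to <12 and 12 to 17 years, zero endogenous FIX: 7.2 and 7.7 days after 50 IU/kg; 10.2 and 11.2 days after 100 IU/kg.

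**The case against.** **Criterion 4 shows what is meant.** It speaks of endogenous FIX and a baseline level, and the other sections can be read as short restatements. That settles the intent. It does not settle what a site must do under Section 11, which uses neither word. Section 11 writes out exceptions to its rule on other FIX products, but none here.

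**Section 8.3 mentions lack of exposure to FIX replacement products before enrolment.** Taken alone, this would exclude every pre-dosed child. But it refers back to criteria that expressly allow up to 3 commercial rFIXFc injections.

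**The reach is narrow.** This stands. Enrolment first needs a local FIX of 2% or less. A local test taken with drug circulating would tend to exceed 2% as well, so that child is not enrolled and never meets Section 11. The harm needs a local value from before exposure, a commercial dose where rFIXFc is marketed, a central draw inside the window, and then enrolment.

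**Sites can avoid the event.** This stands in part. Footnote d in Section 4.2.1 says: "Medical history should also include any dosing with commercially available rFIXFc for bleeding episodes between 28 days prior to Screening". The central draw can be timed within the 8-week screening period. The note on unscheduled visits in the treatment-visit schedule lets sites "repeat any blood sampling if required for study purposes or for local standard of care". None of these steps is required for this purpose, and none overrides a mandatory withdrawal.

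**Eleven days is not the typical figure.** This stands. In children under 6 it needs about 169 IU/kg. Section 5.1.4 reports dose-linear pharmacokinetics only from 12.5 to 100 IU/kg. Low recovery in young children makes such a dose possible under Appendix A, but the time is an extrapolation.

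**Conclusion.** The rule is wrong as written, at minor scale. For doses of 42 to 100 IU/kg in children under 6 with zero endogenous FIX, drug alone keeps the result above 2 IU/dL for about 6 to 9 days. A sample drawn at 72 hours would still read about 4 to 10 IU/dL, so applying the inhibitor sample's washout to the FIX sample would not solve the problem. Some endogenous FIX or repeated doses lengthen the time.

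The times rest on geometric means from 11 previously treated children and a two-exponential curve. Individual children will differ.

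A reader might infer that the rule biases the primary inhibitor proportion, or that many children would be lost. The documents support neither. They give no count of pre-dosed children, the number is likely small, and nothing links this kind of withdrawal to inhibitor risk. An inhibitor-free child who stops early is censored in the Kaplan-Meier analysis and leaves the denominators of exposure-day milestones he did not reach (SAP 9.4.3.3).

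**What to change.** In Section 11, the Synopsis and Sections 7.1, 7.3.1, 8.3 and 9.1.1, state that the 2% withdrawal rule applies to endogenous FIX. Add that, if commercial rFIXFc was given before the central screening sample, a result above 2% does not require withdrawal when a documented pre-exposure FIX value is 2% or less. Section 8.3 already accepts local values from the medical record for enrolment. In SAP 6.2.2.1, use the pre-exposure value for these children.

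Do not require a delayed draw. While eligibility is unconfirmed, bleeds are treated with commercial rFIXFc and count towards the 3-injection limit, and exceeding it makes the child a screen failure (Sections 7.3.1 and 9.1.2). A compulsory wait could lose the child it is meant to keep. A later draw or a retest can be optional, only where clinically safe.

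The cost is one clause in Section 11 and its parallel sections, and one SAP sentence. The downside is that severity rests on a local value for a few children, so a child whose local value was wrong could stay in the study.
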